## 5.2. Exclusion Criteria

A subject will not be eligible for inclusion in this study if any of the following criteria apply:

CONCURRENT CONDITIONS/MEDICAL HISTORY (INCLUDES LIVER FUNCTION AND QTc INTERVAL)

1. Alanine transaminase (ALT) >2xUpper Limit of Normal (ULN) and bilirubin >1.5xULN (isolated bilirubin >1.5xULN is acceptable if bilirubin is fractionated and direct bilirubin <35%).
 
2. Current or chronic history of liver disease, or known hepatic or biliary abnormalities (with the exception of Gilbert's syndrome or asymptomatic gallstones)
 
3. Heart rate corrected QT interval (QTc) > 450 msec or QTc > 480 msec in subjects with Bundle Branch Block
 
NOTES:
 
 
• The QTc is the QT interval corrected for heart rate according to Bazett's formula (QTcB), Fridericia's formula (QTcF), or another method, machine-read or manually over-read.
 
• The specific formula that will be used to determine eligibility and discontinuation for an individual subject should be determined prior to initiation of the study. In other words, several different formulae cannot be used to calculate the QTc for an individual subject and then the lowest QTc value used to include or discontinue the subject from the trial.
 
• For purposes of data analysis, QTcB, QTcF, another QT correction formula, or a composite of available values of QTc will be used as specified in the Reporting and Analysis Plan (RAP).
 
 
4. Asthma exacerbation requiring treatment with oral corticosteroids or hospitalization within 3 months prior to screening
 
5. History of life-threatening asthma, defined as an asthma episode that required intubation and/or was associated with hypercapnea, respiratory arrest or hypoxic seizures within the last 10 years.
 
6. Evidence of concurrent respiratory diseases such as pneumonia, pneumothroax, atelectasis, pulmonary fibrotic disease, allergic bronchopulmonary aspergillosis, cystic fibrosis, bronchopulmonary dysplasia, or other respiratory abnormalities other than asthma.
 
7. Other concurrent diseases/abnormalities: A subject must not have any clinically significant, uncontrolled condition or disease state that, in the opinion of the investigator, would put the safety of the subject at risk through study participation or would confound the interpretation of the efficacy results if the condition/disease exacerbated during the study.
 
8. Respiratory tract infection that is not resolved within 2 weeks prior to screening.

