
## CONCOMITANT MEDICATIONS

9. Treatment with intranasal steroid, inhaled corticosteroid (ICS) with or without long-acting beta2-agonist (LABA), and treatment with non-ICS controller asthma medications (i.e., leukotriene modifier, methylxanthines) within 4 weeks prior to screening.
10. Use of long-acting antihistamines within 7 days' or short-acting antihistamines within 72 hours prior to the screening skin prick test.
11. Treatment with systemic corticosteroids within 6 weeks prior to screening.
12. Use of inhaled SABAs as rescue treatment on average for more than 2 days per week.

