### 7.1.2. Time and Events Table – Dosing visit (DV) 1 (Day 1) – DV8 (Week 8) and Early Withdrawal Visit (EW)

Procedure	Pre-dose	Dose	Post-dose				Early- Withdrawal	Notes
		0 hour	20 mins	1 hour	12 hours	24 hours		
Outpatient visit		X				X	X	Subjects get discharged 1-2 hours after dosing.
Inclusion and exclusion criteria/eligibility review	X							Only on DV1
Diary card collection and review		X					X	Collect and review diary card at every dosing visit
AE/SAE review		X					X	
Concomitant medication review		X					X	
12-lead ECG	X			X		X	X	Perform on DV1 and DV8 only. Not required at EW if this occurs during FU
Vital signs (including temperature)	X 			X 		X 	X	 Perform on DV1-8  Perform on DV1, 4 and DV8 only. Not required at EW if this occurs during FU
Laboratory assessments (include liver chemistries, haematology, clinical chemistry and urinalysis)	X					X	X	Collect samples for laboratory assessments on DV1 and DV8, Not required at EW if this occurs during FU
Blood sample for PK analysis	X		X	X				Collect samples on DV1, DV4 and DV8
Genetic sample		X						Take one sample on any of the dosing visits after genetics consent.
FeNO measurement	X							Perform FeNO measurements pre-dose on all dosing visits 1-8
Nasal examination	X					X		Conducted pre-dose at all study visits and 24 hours post-dose on DV1, DV4 and DV8

Procedure	Pre-dose	Dose	Post-dose				Early-Withdrawal	Notes
			0 hour	20 mins	1 hour	12 hours		
Nasal lavage	X						X	Collect nasal lavage samples pre-dose and 24hrs post-dose on DV1, DV4 and DV8
Blood sample for biomarker analysis	X						X	Collect blood for serum samples and PBMC preparations pre-dose and 24 hrs post-dose on DV1 and DV8
Blood sample for RNA analysis	X 						X 	PAX-gene tubes for TLR7/AFFY chip gene expression in blood collected pre-dose on DV1  and 24 hrs after DV8 
Call RAMOS	X							Randomisation will occur is at Visit 1 via the IRT. Sites should also call RAMOS at DV5.
Dispensing of study medication	X							One device will be assigned on DV1. The second device will be assigned on DV5. All devices remain in the unit.
Study drug administration		X						All doses are administered in the unit.

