## 7.4. Safety

Planned time points for all safety assessments are listed in the Time and Events Table (Section 7.1). Additional time points for safety tests (such as vital signs, physical exams and laboratory safety tests) may be added during the course of the study based on newly available data to ensure appropriate safety monitoring.

The Safety Review Team (SRT) is a GSK cross-functional team reviewing all available safety data related to the project, including in-stream data from this study, in an ongoing manner. The SRT is an internal GSK requirement put in place to ensure holistic evaluation of the safety profile of an investigational product with systematic, periodic and documented reviews of available safety data, with the appropriate communication and escalation of new findings that have the potential to impact patient safety.

The SRT for this project will review data from this study in collaboration with an independent external (to GSK) expert reviewer.

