**Table 1 Protocol Required Safety Laboratory Assessments**

Laboratory Assessments	Parameters							
Haematology	Platelet Count		RBC Indices:	White Blood Cell (WBC) count with Differential:				
	Red Blood Cell (RBC) Count		Mean Corpuscular Volume (MCV)	Neutrophils				
	Hemoglobin		Mean corpuscular hemoglobin (MCH)	Lymphocytes				
	Hematocrit			Monocytes				
				Eosinophils				
				Basophils				
Clinical Chemistry 	Blood Urea Nitrogen (BUN)	Potassium	AST (SGOT)	Total and direct bilirubin				
	Creatinine	Sodium	ALT (SGPT)	Total Protein				
	Glucose	Calcium	Alkaline phosphatase	Albumin				
Routine Urinalysis	
 
Specific gravity
 
pH, glucose, protein, blood and ketones by dipstick
 
Microscopic examination (if blood or protein is abnormal)
 
							
Other Screening Tests	
 
HIV
 
Hepatitis B (HBsAg)
 
Hepatitis C (Hep C antibody)
 
FSH and estradiol (as needed in women of non-child bearing potential only)
 
Alcohol and drug screen (to include at minimum: amphetamines, barbiturates, cocaine, opiates, cannabinoids and benzodiazepines)
 
Urine hCG Pregnancy test 
 
							
NOTES :								

 
Details of Liver Chemistry Stopping Criteria and Required Actions and Follow-Up Assessments after liver stopping or monitoring event are given in Section 5.4.1 and Appendix 2.
 
Local urine testing will be standard for the protocol unless serum testing is required by local regulation or ethics committee.
 
								

All laboratory tests with values that are considered clinically significantly abnormal during participation in the study should be repeated until the values return to normal or baseline. If such values do not return to normal within a period judged reasonable by the investigator, the etiology should be identified and the sponsor notified.

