## 12.2. Appendix 2: Liver Safety Required Actions and Follow up Assessments

### Phase II Liver Chemistry Stopping and Increased Monitoring Algorithm

### Phase II liver chemistry increased monitoring criteria with continued therapy

Liver Chemistry Increased Monitoring Criteria – Liver Monitoring Event	
Criteria	Actions
ALT ≥ 3xULN and <5xULN and bilirubin <2xULN, without symptoms believed to be related to liver injury or hypersensitivity, and who can be monitored weekly for 4 weeks	
 
Notify the GSK medical monitor within 24 hours of learning of the abnormality to discuss subject safety.
 
Subject can continue study treatment
 
Subject must return weekly for repeat liver chemistries (ALT, AST, alkaline phosphatase, bilirubin) until they resolve, stabilise or return to within baseline
 
If at any time subject meets the liver chemistry stopping criteria, proceed as described above
 
If, after 4 weeks of monitoring, ALT <3xULN and bilirubin <2xULN, monitor subjects twice monthly until liver chemistries normalize or return to within baseline.
 

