
e. Is a congenital anomaly/birth defect
 
f. Other situations:
 

• Medical or scientific judgment should be exercised in deciding whether reporting is appropriate in other situations, such as important medical events that may not be immediately life-threatening or result in death or hospitalization but may jeopardize the subject or may require medical or surgical intervention to prevent one of the other outcomes listed in the above definition. These should also be considered serious.

• Examples of such events are invasive or malignant cancers, intensive treatment in an emergency room or at home for allergic bronchospasm, blood dyscrasias or convulsions that do not result in hospitalization, or development of drug dependency or drug abuse

g. Is associated with liver injury and impaired liver function defined as:
 

• ALT <math>\geq 3 \times \text{ULN}</math> and total bilirubin* <math>\geq 2 \times \text{ULN}</math> (<math>>35\%</math> direct), or

• ALT <math>\geq 3 \times \text{ULN}</math> and International Normalised Ratio (INR)** <math>> 1.5</math>.

 
* Serum bilirubin fractionation should be performed if testing is available; if unavailable, measure urinary bilirubin via dipstick. If fractionation is unavailable and ALT <math>\geq 3 \times \text{ULN}</math> and total bilirubin <math>\geq 2 \times \text{ULN}</math>, then the event is still to be reported as an SAE.
 
** INR testing not required per protocol and the threshold value does not apply to subjects receiving anticoagulants. If INR measurement is obtained, the value is to be recorded on the SAE form.
 

• Refer to Appendix 2 for the required liver chemistry follow-up instructions

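### Exclusion criterion 1 joins its ALT and bilirubin limits with 'and', so as written it does not exclude an isolated ALT above 2xULN, and its bracket does not fit the connector

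*Protocol*

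**What the plan says.** Protocol 5.2, criterion 1, excludes a subject with ALT above "2xUpper Limit of Normal (ULN) and bilirubin" above 1.5xULN. The bracket that follows says isolated bilirubin above 1.5xULN "is acceptable if bilirubin is fractionated and direct bilirubin" is below 35%. Any one numbered criterion is enough to exclude, and Protocol section 5 allows no deviations from the criteria.

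Two other criteria in 5.2 could touch the same subjects. Criterion 2 covers liver disease and known hepatic or biliary abnormalities, with Gilbert's syndrome and symptomless gallstones excepted. Criterion 7 covers clinically significant uncontrolled conditions in the investigator's opinion. Neither gives an ALT or bilirubin value. The amendment history in Protocol Appendix 7 lists no change to criterion 1.

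In the SAP, Appendix 7 (11.7.1) gives ALT at or above 2xULN and total bilirubin at or above 1.5xULN as separate liver concern ranges, with the combination as a further row. Section 7.1.1 bases the primary efficacy analysis on the Per Protocol population. Appendix 1 (11.1.1) expects a subject enrolled despite an eligibility failure to be left out of that population, decided case by case.

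**The concern.** The two halves of the criterion point in different directions. If both abnormalities are needed to exclude, bilirubin alone never excludes, and a conditional concession for it is not needed. If the concession is needed, bilirubin alone must be able to exclude, and then the connector should be 'or'. The bracket hints at the answer for bilirubin but is silent on ALT alone.

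The rest of the protocol does not settle the matter, because it uses the word both ways. Criterion 9 uses 'and' to string together separate exclusions: "and treatment with non-ICS controller asthma medications (i.e., leukotriene modifier, methylxanthines) within 4 weeks prior to screening". The Appendix 2 monitoring band uses it as a true conjunction: "ALT ≥ 3xULN and <5xULN and bilirubin <2xULN, without symptoms believed to be related to liver injury or hypersensitivity". So does item g of the SAE definition in 12.4.3 ("Is associated with liver injury and impaired liver function defined as"), which pairs ALT with bilirubin or with INR.

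At stake is whether a subject with a raised screening ALT and normal bilirubin may be enrolled. With no deviations allowed, a site has reason to apply the words as they stand, and that is the weaker safety rule.

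**Working it through.** No sample size, power or error rate is involved, so the check is a truth table.

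**Inputs.** From Protocol 5.2, criterion 1: the ALT limit (2xULN), the bilirubin limit (1.5xULN), the connector, and the bracket's condition on direct bilirubin (35%). I take 'isolated' bilirubin to mean raised bilirubin with ALT not above 2xULN. Two ALT states times three bilirubin states give 2 x 3 = 6 patterns.

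**Readings compared.**
- A: 'and', with the bracket only granting permission.
- B: 'and', with the bracket also implying that isolated bilirubin failing its condition is not acceptable.
- C: 'or', with the bracket as an exception to the bilirubin limit.

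Result under criterion 1 alone:

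| ALT | Bilirubin | A | B | C |
|---|---|---|---|---|
| <=2x | <=1.5x | eligible | eligible | eligible |
| <=2x | >1.5x, direct <35% | eligible | eligible | eligible |
| <=2x | >1.5x, direct >=35% or not fractionated | eligible | excluded | excluded |
| >2x | <=1.5x | eligible | eligible | excluded |
| >2x | >1.5x, direct <35% | excluded | excluded | excluded |
| >2x | >1.5x, direct >=35% or not fractionated | excluded | excluded | excluded |
| **Excluded** | | **2 of 6** | **3 of 6** | **4 of 6** |

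**What the bracket does.** Without the bracket, 'and' excludes 2 patterns and 'or' excludes 5. Under A the bracket changes 2 - 2 = 0 patterns. Under B it adds 3 - 2 = 1 exclusion that the main clause does not contain. Under C it removes 5 - 4 = 1 exclusion, which is what a concession normally does.

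**Where the readings part.** A and C differ in 4 - 2 = 2 patterns: isolated ALT above 2xULN, and isolated bilirubin with direct share of 35% or more or not fractionated. B and C differ in 4 - 3 = 1 pattern: isolated ALT above 2xULN. So isolated ALT is admitted under either treatment of the bracket while 'and' stands; the bilirubin pattern turns on how the bracket is read.

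**Against the SAP.** A subject with isolated ALT above 2xULN passes criterion 1 on the literal reading, yet that value already lies in the SAP's stand-alone ALT concern range.

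**Per Protocol link.** Under A or B, enrolling that subject is no eligibility failure. Under C it is, and removal is expected subject to case-by-case review. Protocol 4.3 plans 20 completers per arm, so one subject is 1/20 = 5% of an arm.

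**The case against.** The best defence is that the intended meaning can be recovered. The bracket signals that bilirubin can exclude alone, criterion 9 shows 'and' used as a list in the same section, and the SAP's separate ranges suggest that each limit matters alone. The conjunctive examples are an on-treatment monitoring band and an SAE definition, not eligibility rules. This makes 'or' the likelier intention. It does not make it the text, and nothing in the bracket speaks to ALT alone.

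A second defence stands in part. A reader might infer that the bracket is wholly without function under 'and'. That follows only if the bracket is pure permission. Saying that something is acceptable under a condition naturally implies that it is otherwise unacceptable, and then the bracket does some work beside 'and'. The firm divergence is therefore isolated ALT; the bilirubin pattern is only unclear.

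A reader might also infer that the wording leaves subjects with raised ALT unmonitored through most of dosing, since the schedule says "Collect samples for laboratory assessments on DV1 and DV8". The documents do not support tying that to criterion 1. The schedule is the same for every subject, and both visits sample before and 24 hours after dosing. Clinically significant laboratory "values that are considered clinically significantly abnormal during participation in the study should be repeated until the values return to normal or baseline", and Protocol 7.4 says "Additional time points for safety tests (such as vital signs, physical exams and laboratory safety tests) may be added". Appendix 2 prescribes weekly chemistries for ALT from 3xULN to below 5xULN with bilirubin below 2xULN and no suggestive symptoms. Its stopping algorithm is not in the text available here, so what it requires for bilirubin cannot be judged.

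Finally, the risk table in Protocol 4.6.1 names no hepatic risk for this product, the dose is 20 ng intranasally once a week, and SAP 8.3.3.1 expects plasma concentrations to be non-quantifiable. That stands, and it keeps the severity low.

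**Conclusion.** Criterion 1 is wrong as written, with minor severity. The connector and the bracket do not fit together. While 'and' stands, criterion 1 does not exclude an isolated ALT above 2xULN, and it leaves open whether isolated bilirubin above 1.5xULN is excluded when the direct share is 35% or more or was not measured. Criteria 2 and 7 may catch some of these subjects, but through history or judgement rather than a number.

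The documents give no frequency for such results, so I put no figure on it. My judgement, given a population described as in good general health, is that few subjects would be affected and possibly none. There is no evidence that sites have in fact diverged. A reader might infer either that the trial's validity is threatened or that the primary analysis cannot be touched. Neither is supported: the numbers are likely to be very small, but an individual's eligibility, and with it Per Protocol membership, could turn on the reading chosen.

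The conclusion assumes that 'isolated' means without ALT above 2xULN and that sites work from the protocol text alone.

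**What to change.** Replace 'and' with 'or' in criterion 1: exclude if ALT is above 2xULN, or if bilirubin is above 1.5xULN, with isolated bilirubin above 1.5xULN acceptable when it is fractionated and direct bilirubin is below 35%. The bracket then acts as an ordinary exception to the bilirubin limit, and isolated ALT is covered.

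The cost is a one-word change at the next protocol amendment. No assessment is added: liver chemistries are already taken at Screening Visit 1 (Protocol 7.1.1), and the chemistry panel in Protocol Table 1 already contains ALT and total and direct bilirubin.

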
## CONCOMITANT MEDICATIONS

9. Treatment with intranasal steroid, inhaled corticosteroid (ICS) with or without long-acting beta2-agonist (LABA), and treatment with non-ICS controller asthma medications (i.e., leukotriene modifier, methylxanthines) within 4 weeks prior to screening.
10. Use of long-acting antihistamines within 7 days' or short-acting antihistamines within 72 hours prior to the screening skin prick test.
11. Treatment with systemic corticosteroids within 6 weeks prior to screening.
12. Use of inhaled SABAs as rescue treatment on average for more than 2 days per week.

## RELEVANT HABITS

13. History of regular alcohol consumption within 6 months of the study defined as: An average weekly intake of **>14 units for males and females**. One unit is equivalent to 8 g of alcohol: a half-pint (~240 ml) of beer, 1 glass (125 ml) of wine or 1 (25 ml) measure of spirits.

## CONTRAINDICATIONS

14. Patient known to be intolerant to salbutamol or albuterol
15. History of sensitivity to any of the study medications, or components thereof or a history of drug or other allergy that, in the opinion of the investigator or GSK Medical Monitor, contraindicates their participation.

## DIAGNOSTIC ASSESSMENTS AND OTHER CRITERIA

16. Presence of hepatitis B surface antigen (HBsAg), positive hepatitis C antibody test result at screening or within 3 months prior to first dose of study treatment. For potent immunosuppressive agents, subjects with presence of hepatitis B core antibody (HBcAb) should also be excluded.
17. A positive pre-study drug/alcohol screen
18. A positive test for Human Immunodeficiency Virus (HIV) antibody
19. Where participation in the study would result in donation of blood or blood products in excess of 500 mL within a 56 day period.
20. The subject has participated in a clinical trial and has received an investigational product within the following time period prior to the first dosing day in the current study: 30 days, 5 half-lives or twice the duration of the biological effect of the investigational product (whichever is longer)
21. Exposure to more than 4 investigational medicinal products within 12 months prior to the first dosing day

### 5.3. Screening Failures/Re-screening

Screen failures are defined as subjects who consent to participate in the clinical trial but are never subsequently randomized. In order to ensure transparent reporting of screen failure subjects, meet the Consolidated Standards of Reporting Trials (CONSORT) publishing requirements, and respond to queries from Regulatory authorities, a minimal set of screen failure information is required including Demography, Screen Failure details, Eligibility Criteria, and Serious Adverse Events (see Section 7.4.1.6).

Re-screening will be permitted in this study, in discussion with the Medical Monitor. Sites are encouraged to screen subjects who have previously undergone BAC and have demonstrated a LAR.

Re-screened subjects should be assigned a separate number from their initial screening number and complete a new informed consent form.

### 5.4. Withdrawal/Stopping Criteria

Reasons for withdrawal from the study may include:

- Use of a prohibited medication that cannot be safely discontinued while maintaining the subject's health.
- Treatment code is unblinded.
- Pregnancy: Any female subject who becomes pregnant.

The following actions must be taken in relation to a subject who fails to attend the clinic for a required study visit:

- The site must attempt to contact the subject and re-schedule the missed visit as soon as possible.
- The site must counsel the subject on the importance of maintaining the assigned visit schedule and ascertain whether or not the subject wishes to and/or should continue in the study.
- In cases where the subject is deemed 'lost to follow up', the investigator or designee must make every effort to regain contact with the subject (where possible, 3 telephone calls and if necessary a certified letter to the subject's last known mailing address or local equivalent methods). These contact attempts should be documented in the subject's medical record.
- Should the subject continue to be unreachable, only then will he/she be considered to have withdrawn from the study with a primary reason of "Lost to Follow-up".

A subject may withdraw from study treatment at any time at his/her own request, or may be withdrawn at any time at the discretion of the investigator for safety, behavioural or administrative reasons. If a subject withdraws from the study, he/she may request destruction of any samples taken, and the investigator must document this in the site study records.

Subjects withdrawn from the study while already exposed to IP will be asked to complete all safety assessments as outlined in the Time and Events Table (Section 7.1.2). Relevant pages of the case report form (CRF) should be completed by the investigator.

The replacement of withdrawn subjects will be at the discretion of the sponsor. If a subject misses one treatment dose, the investigator will consult with the GSK medical monitor as to whether the subject can receive further treatment. If more than one treatment dose is missed, then the subject may be withdrawn from the study, at the discretion of the Sponsor, in consultation with the investigator.

If subjects prematurely discontinue the study, additional replacement subjects may be recruited and assigned the next available randomisation number, at the discretion of the Sponsor, in consultation with the investigator.

